A bone marrow examination is required to confirm Complete Remission (CR) at least 2 months after completion of therapy and when a subject fulfills the International Workshop for Chronic Lymphocytic Leukemia (IWCLL) updated National Cancer Institute-Sponsored Working Group (NCI-WG) requirements for Complete Remission (CR) [Hallek, 2008]. Previous results may be used or if not available, a bone marrow exam may be done at screening. If a subject's response improves to a CR while on study, then a bone marrow examination is required to confirm CR at least 2 months after response as per the updated IWCLL NCI-WG requirements for CR [Hallek, 2008]. Additionally, CT Scans are required at screening, for confirmation of a new CR, yearly while on study, and at disease progression.

Study Endpoints/Assessments

Primary Endpoint:

- Progression free survival (PFS), defined as the interval from randomization until disease progression or death

Secondary Endpoints:

Clinical

- Improvement in response
- Time to next treatment
- Overall survival
- Progression-free survival after next-line therapy

- Time to progression after next-line therapy
- Changes in patient reported outcome (PRO) measures
- Changes in patient reported outcome (PRO) scores
- Improvement of ECOG performance status
- B-symptoms/Constitutional symptoms/fatigue
- Incidences of and number of subjects with grade 3 and 4 infections
- Incidence, severity of adverse events, serious adverse events and other safety parameters
- Evaluation of myelosuppression (anemia, neutropenia, thrombocytopenia)
- Frequency of transfusions
- Incidence of Autoimmune Hemolytic Anemia (AIHA)
- Human Anti Human Antibodies (HAHA)
- IgG, IgA, IgM serum levels

Disease markers

- Minimal Residual Disease (MRD)
- B-cell monitoring
- Prognostic markers correlating with clinical response:
 - Cytogenetics by fluorescent in situ hybridization (FISH)
 - IgV_H mutational status
 - β 2 microglobulin
 - Changes in complement levels

Pharmacokinetics

- Plasma ofatumumab concentrations

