6.1.8. Concomitant Medication

Any medication other than the trial drug is considered concomitant medication (apart from protocol defined premedication given prior to the infusions of ofatumumab) and will be documented, including the following information:

- Indication

- Dose information
- Start date
- Stop date of administration or ongoing at study termination

Of note: Intravenous gamma globulin, prophylactic antibiotics, and G-CSF may be given per local standard of care, at the physician's discretion.

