6.3.4. Peripheral Blood Sampling for Safety and Disease Status

The following laboratory tests will be performed:

- Direct antiglobulin test (Coombs test) at screening and 3 months after last treatment.
- Hepatitis B (HBV) and Hepatitis C (HCV) at screening.

For subjects that are HBsAg negative, HBcAb positive and HBV DNA negative (see Section 4.3) blood samples will be collected for HBV DNA testing every 2 months during the treatment/observation and during follow-up at the 3 months and 6 months visit.

- Screening pregnancy test (HCG) for women of childbearing potential, unless they have had a hysterectomy, have undergone tubal ligation within one year before the screening visit, or have been postmenopausal for at least one year.
- Human Anti-Human Antibody (HAHA) prior to first dose of ofatumumab, every 6 months during ofatumumab treatment, and at 3 and 6 months post treatment (i.e. predose Visit 1, at Months 7, 13, 19, and 25 during treatment and at 3 and 6 months after last ofatumumab dose, regardless of when it occurs). A HAHA sample (and a pharmacokinetic sample) should also be obtained at the last treatment visit if it does not occur at a scheduled sampling time (e.g., if treatment is discontinued early). HAHA samples will only be collected for subjects randomized to ofatumumab.
- Complement: CH50 at baseline and after last treatment visit.
- IgA, IgG and IgM at screening, every 6 months during treatment, and after last treatment visit and/or upon relapse. In case of infection, these immunoglobulins may be tested at the physician's discretion. Additional samples may be collected post last treatment (such as 3 and 6 months f/u), if warranted.

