- Situations where an untoward medical occurrence did not occur (social and/or convenience admission to a hospital)
- Anticipated day-to-day fluctuations of pre-existing disease(s) or condition(s) present or detected at the start of the study that do not worsen
- B cell depletion and hypogammaglobulinemia due to ofatumumab treatment

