6.4.6. Laboratory and Other Safety Assessment Abnormalities Reported as AEs and SAEs

Any abnormal laboratory test results (hematology, clinical chemistry, or urinalysis) or other safety assessments (e.g., ECGs, vital signs measurements), including those that worsen from baseline, and felt to be clinically significant in the medical and scientific judgement of the investigator are to be recorded as AEs or SAEs.

However, any clinically significant safety assessments that are associated with the underlying disease, unless judged by the investigator to be more severe than expected for the subject's condition, are **not** to be reported as AEs or SAEs.

B cell depletion, IgG below LLN, low CD19+ count, and hypogammaglobulinemia due to treatment with ofatumumab are **not** to be reported as AEs or SAEs.

Infusion related AEs may lead to a prolonged infusion time. Overnight stay at the hospital due to slow infusion rate is **not** to be reported as a SAE.

Specific attention will be paid to monitor events of special interest such as infusion reactions, tumor lysis syndrome, infections and progressive multifocal leukoencephalopathy (PML). Please refer to the SPM and/or the following text*.

Handling Infusion Reactions:

Infusion reactions are commonly associated with anti-CD20 antibody therapy. Ofatumumab can cause serious infusion reactions manifesting as bronchospasm, dyspnea, laryngeal edema, pulmonary edema, flushing, hypertension, hypotension, syncope, cardiac ischemia/infarction, back pain, abdominal pain, pyrexia, rash, urticaria, and angioedema. Infusion reactions occur more frequently with the first 2 infusions.

The site staff must be prepared to intervene if an infusion reaction occurs. Special caution should be taken during the first infusion for each subject and during the infusion for any subject who did not tolerate a previous infusion well. It is recommended that a crash cart is readily accessible in the event of an emergency. Infusion reactions should be treated according to the investigators judgment and best clinical practice.

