The number and percentage of subjects who receive blood transfusions during the study will be provided by treatment group.

- Incidence of Autoimmune Hemolytic Anemia (AIHA)

The number and percentage of subjects with autoimmune hemolytic anemia during the study will be provided by treatment group. The proportion of subjects with AIHA will be compared between treatment groups with the Cochran-Mantel-Haenszel test adjusting for stratification factors (response at entry, number of prior treatments and type of prior treatment).

- Human Anti-Human Antibodies (HAHA)

HAHA sample analysis will be conducted by a contract research organization using a validated assay. The number and percentage of subjects with positive and negative

HAHA results will be provided for each HAHA timepoint. A summary table with the overall HAHA assessment for each subject, considering ofatumumab concentration at the time of each HAHA sample collection, will be provided. A listing of HAHA results with the ofatumumab concentration at that time will be provided

- IgG, IgA, IgM

Summaries of IgG, IgA, and IgM will be provided at scheduled visits for actual values as well as for change from baseline.

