Listings for lab data for subjects with abnormalities of potential clinical concern will be provided. Figures for median hemoglobin/neutrophil count/platelet count for all subjects, and for all subjects excluding those who received blood supportive care products over time will also be generated.

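### IgG summaries have no rule for values taken after immunoglobulin replacement, so they may understate an ofatumumab-related fall that AE reporting also leaves out

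*SAP*

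**What the plan says.** The protocol summary lists "IgG, IgA, IgM serum levels" among the secondary endpoints. Protocol section 6.3.4 schedules "IgA, IgG and IgM at screening, every 6 months during treatment, and after last treatment visit and/or upon relapse". It also allows extra tests during infection at the physician's discretion.

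The SAP analysis is one sentence in section 11.2: "Summaries of IgG, IgA, and IgM will be provided at scheduled visits for actual values as well as for change from baseline". Section 8 keeps all data up to study completion or withdrawal, and section 9.2.9 confines unscheduled values to worst-case displays and listings. In the output lists this becomes:

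- Tables 3.1090 (levels over time) and 3.1100 (change from baseline);
- Table 3.1091 (levels up to 60 days after last treatment), in the 280-event list only;
- Figure 13.0070 (median IgG), with 13.0080 and 13.0090 for IgA and IgM;
- Listing 23.0340 (subject-level values).

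On replacement, protocol section 6.1.8 says: "Of note: Intravenous gamma globulin, prophylactic antibiotics, and G-CSF may be given per local standard of care, at the physician's discretion". Such use is recorded as concomitant medication, with indication and dates.

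On AE reporting, section 6.4.3 lists "B cell depletion and hypogammaglobulinemia due to ofatumumab treatment" among events that are not AEs. Section 6.4.6 adds that "B cell depletion, IgG below LLN, low CD19+ count, and hypogammaglobulinemia due to treatment with ofatumumab are" not reportable as AEs or SAEs.

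For blood counts, SAP section 12.7 plans median hemoglobin, neutrophil and platelet figures both for all subjects and "for all subjects excluding those who received blood supportive care products over time". Those repeat figures are 13.0110 to 13.0130 in the 280-event list.

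**The concern.** Infused immunoglobulin is counted in measured IgG. If a subject's IgG falls on ofatumumab and replacement is started, later scheduled values reflect the drug effect plus the replacement, and the plan pools them with unsupported values. The SAP recognises this problem for the three blood counts, but Figure 13.0070 has no counterpart.

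For most laboratory effects the AE tables offer a second view. Here they do not, because the effect is excluded from reporting when attributed to ofatumumab. That clause can apply only to the arm that receives the drug. The separate exclusion of disease-associated findings, which excepts those more severe than expected, applies to both arms. An AE comparison therefore cannot replace the IgG displays and could itself favour ofatumumab.

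At stake is an accurate description of IgG loss over two years of B-cell-depleting treatment, in a trial where infections are an event of special interest. No efficacy conclusion depends on it.

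**Working it through.** There is no stated figure to reproduce: the IgG analysis is descriptive and carries no sample size, power or test. The check has two parts.

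**1. Does any planned output close the gap?**

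- *IgG displays.* None of Tables 3.1090, 3.1091 and 3.1100 or Figure 13.0070 is specified with a replacement rule. The SAP for the final analysis keeps 3.1090, 3.1100, 13.0070 and 23.0340 and omits 3.1091. The listing gives individual values, not an arm comparison.
- *Out-of-range summaries.* SAP section 9.4.1 promises these for laboratory tests not in CTCAE. The listed out-of-range tables (3.0970 and 3.1030) cover chemistry and hematology only. A simple below-LLN count would also miss subjects whom replacement had lifted above LLN.
- *Concomitant medications.* SAP section 10.5 and Table 1.4240 count users by ingredient, without a link to IgG. Section 9.3.1 sets the start and end flags to BEFORE if a subject has taken no study treatment, and the summaries require an end flag of DURING or AFTER. Read literally, this drops every observation-arm record, although section 9.3 defines an on-treatment period for that arm from randomization. A count of replacement by arm is therefore not assured. The blood supportive care summaries use the same flags.

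**2. How large could the distortion be?** The share replaced, the rise in IgG and the SD of IgG change are not in the documents, so all are assumed.

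*Simple shift of one arm's mean* = share on replacement × rise in IgG:

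- 0.05 × 2 g/L = 0.1 g/L
- 0.10 × 2 g/L = 0.2 g/L
- 0.10 × 4 g/L = 0.4 g/L
- 0.20 × 4 g/L = 0.8 g/L

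The distortion of the between-arm difference is (ofatumumab share − observation share) × rise. With shares of 0.10 and 0.05 and a rise of 2 g/L it is 0.1 g/L. With equal shares it is zero.

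*Selective replacement.* Let IgG change be normal with mean −μ in SD units. A share p, those with the largest falls, is replaced and returns to zero change. With z the p-quantile of the standard normal and φ its density:

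- observed mean fall = μ(1 − p) − φ(z)
- observed median fall = μ − z(0.5 + p), where z(0.5 + p) is the (0.5 + p)-quantile

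For μ = 1 and p = 0.10: 0.900 − 0.1755 = 0.725 SD.

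| Share replaced | Mean fall, μ = 1.0 | Median fall, μ = 1.0 | Mean fall, μ = 0.5 |
|---|---|---|---|
| 2% | 0.932 | 0.950 | 0.442 |
| 5% | 0.847 | 0.874 | 0.372 |
| 10% | 0.725 | 0.747 | 0.275 |
| 20% | 0.520 | 0.476 | 0.120 |
| 30% | 0.352 | 0.158 | 0.002 |

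If replaced subjects are unrelated to the size of the fall, the observed mean is μ(1 − p), so it shrinks only by the replaced share.

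*Would excluding post-replacement values repair it?* In the same model the mean fall after exclusion is μ − φ(z)/(1 − p):

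- p = 0.10: 1 − 0.1755/0.9 = 0.805 SD. The bias is 0.195, against 0.275 with all values, so about 71% remains.
- p = 0.20: 1 − 0.2800/0.8 = 0.650 SD. The bias is 0.350, against 0.480, so about 73% remains.

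With a fixed rise instead of a return to baseline, exclusion can be worse than inclusion. At p = 0.10 and a rise of 2 g/L, inclusion biases the mean by 0.2 g/L and exclusion by 0.195 SD. Exclusion is then worse once the SD of change exceeds 0.2/0.195, about 1.0 g/L. For a rise of 4 g/L the threshold is about 2.1 g/L.

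**The case against.** A reader might infer that the plan hides drug-induced hypogammaglobulinemia in the only table able to show it, and that the between-arm IgG difference is biased toward no harm. The documents do not support this. IgG appears in several tables, a figure and a subject-level listing, at scheduled visits. IgA and IgM are shown alongside. Gamma globulin is allowed in both arms, so the between-arm effect depends on the difference in use and could be nil. The documents do not say that replacement goes mainly to subjects whose IgG has fallen, and its size is unknown.

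Three further objections have weight. The IgG summaries are descriptive, no between-arm test is specified, and the 280-event and final plans call their results descriptive. Infection is captured directly: protocol section 6.4.3 requires every infection to be reported as an AE, and the SAP tabulates infections at length. The blood-count precedent is limited, being figures only, and the final-analysis list omits the supportive-care-excluded versions.

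These points lower the stakes and rule out claims of proven masking. They do not supply a rule for post-replacement IgG, an assured count of replacement by arm, or another comparative view of drug-related low IgG.

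**Conclusion.** The concern holds in limited form. As written, the IgG level and change displays mix values before and after replacement, and the AE tables cannot supply what is lost. If any ofatumumab subjects are replaced after a fall, that arm's fall is understated. In the illustrative model the effect runs from slight (0.93 of a true 1.0 SD fall at 2% replaced) to severe (0.35 at 30%). The direction within the arm follows from replacement raising IgG. The size rests on an assumed replacement share, assumed selection of the largest fallers and a normal model. The direction and size of any between-arm bias cannot be stated without replacement rates in both arms.

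This is a gap in reporting a secondary safety endpoint. It does not affect the PFS result or the infection tables. It is worth closing because the remedy is cheap and the medication data are already collected.

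**What to change.** In SAP section 11.2 and the output lists that carry Tables 3.1090 and 3.1100 and Figure 13.0070:

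1. Add, by arm and scheduled visit including baseline, the number and percentage of subjects with IgG below LLN or immunoglobulin replacement started. Replacement cannot hide an event in this measure. Baseline is needed because subjects may enter with low IgG.
2. Report by arm the number starting replacement, counting from randomization in the observation arm so that the BEFORE flag in section 9.3.1 does not remove those subjects.
3. Keep the all-values level and change summaries. Add a version excluding values after first replacement only as a supportive display, noting that it removes subjects likely to have the largest falls and so remains biased toward no fall.
4. Footnote the IgG displays to say that AE tables do not capture hypogammaglobulinemia attributed to ofatumumab, citing protocol sections 6.4.3 and 6.4.6.

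The cost is SAP wording, a merge with concomitant-medication records and a few extra displays. Trial conduct does not change. One limit remains: replacement is discretionary in an open-label trial, so the measure in item 1 partly reflects prescribing practice. Showing its two components separately lets the reader judge this.

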#### **Disease Markers:**

- Minimal Residual Disease (MRD)

The number and percentage of subjects with positive and negative MRD will be provided at each timepoint. The proportion of subjects with negative MRD and positive MRD will be compared between treatment groups with the Cochran-Mantel-Haenszel test adjusting for stratification factors (response at entry, number of prior treatments and type of prior treatment). An analysis of the time to first MRD positivity for subjects who were MRD negative at baseline will also be provided using Kaplan-Meier methodology.

- B-cell monitoring

The change and percent change of  $CD5^+CD19^+$  and  $CD5^-CD19^+$  from baseline will be summarized to assess the treatment effect, to monitor the normal B-cell population, and to follow their recovery. In addition, frequency and percentage of subjects with complete B-cell depletion and near-complete B-cell depletion will be summarized. Complete B-cell depletion is defined as the absolute value of  $CD5^+CD19^+$  and  $CD5^-CD19^+$  both equal to zero cells/uL. Near complete B-cell depletion is defined as the sum of the absolute value of  $CD5^+CD19^+$  and  $CD5^-CD19^+$   $<5$  cells/uL.

Tables that will be provided are:

- Summary of  $CD5^+CD19^+$  counts over time
- Summary of  $CD5^-CD19^+$  counts over time
- Summary of  $CD5^+CD19^+$  change from baseline (counts and percentage)
- Summary of  $CD5^+CD19^+$  percent change from baseline (counts and percentage)
- Summary of  $CD5^-CD19^+$  change from baseline (counts and percentage)
- Summary of  $CD5^-CD19^+$  percent change from baseline (counts and percentage)
- Summary of subjects with complete B-cell depletion Summary of subjects with near-complete B-cell depletion
- Prognostic markers correlating with clinical response

Cox-regression will be used to explore the relationship between PFS and the following explanatory variables: treatment group, cytogenetics (analyzed by FISH) at baseline,

IgVH mutational status at baseline,  $\beta$ 2 microglobulin at baseline, baseline CD20 and baseline complement level. Ctau and Cmax at Cycle 1 Day 1, Cycle 1 Day 8, and Cycle 4 and cytogenetics at relapse may also be considered as possible explanatory variables in the model.

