6.2.3. Minimal Residual Disease (MRD)

For subjects enrolling in the study who are in CR, baseline MRD will be assessed at screening, prior to any treatment visit.

For subjects who improve to a CR while on study, a bone marrow examination will be performed after at least 2 months of therapy or response while on study.

The bone marrow sample if available, and/or peripheral blood sample will be examined by flow cytometry with the following B-CLL MRD panel [Rawston, 2007]:

- CD5/CD19 with CD20/CD38
- CD5/CD19 with CD81/CD22
- CD5/CD19 with CD79b/CD43

In addition CD3/CD19 with CD14/CD45 analysis is performed to allow enumeration of CD19+ cells and contamination assessment and CD5/CD19 with Igλ/Igκ analysis is performed to confirm clonality.

Subjects with negative MRD will receive follow-up MRD assessments of the peripheral blood until MRD analysis becomes positive.

The absence of MRD is defined as less than one B-CLL cell per 10,000 leukocytes.

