6.3.1.2. B-Cell Monitoring

B-cell monitoring (CD5⁺CD19⁺ and CD5⁻CD19⁺) will be performed every two months and at every follow-up visit until values return to normal levels on two consecutive determinations.

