11. APPENDICES

11.1. Appendix 1: Time and Events

Phase	SCREEN	Treatment or Observation (~ every 8 wks after 1 st visit)			Follow-up (every 3 months for 5 years)	WD
		1	2	3-14		
Visit	Screening	1	2	3-14	15-34	
Week	(-6 to -1)	1	2	9-97	109-337	
Month	0	1	1	3-25	28-85	
Visit Window		± 7d	± 3d	± 7d	± 14d	
Administration of Ofatumumab (if assigned to treatment group)		X	X	X		
Informed Consent	X					
Eligibility Criteria	X					
Demographics	X					
Medical History ¹	X					
Height	X					
Body weight	X		X	X	X	X
Physical Exam	X		X	X	X	X
Lymph node evaluation	X		X	X	X	X
Organ Evaluation	X		X	X	X	X
ECOG	X		X	X	X	X
ECG	X					
Adverse Event Assessments		X	X	X	X ¹²	X
Concomitant Medications		X	X	X	X ¹²	X
CT Scan	X			X ²	X ²	X
Bone marrow biopsy	X ³			X ³		
Flow cytometry (MRD)	X ³			X ³	X ³	X ³
Flow cytometry(CD5/CD19)	X			X	X ⁴	X
Prognostic Factors ⁵	X					X
Response Evaluation		X	X	X	X	X
PRO	X			X	X	X
Hematology ⁶	X	X	X	X	X	X
Biochemistry ⁶	X	X	X	X	X	X
Hepatitis ⁷ and Pregnancy Test	X					
Igs	X			X ^{8,9}		
HABA ¹⁰		X		X ^{8,9}	X ⁹	X
Coombs and CH50	X				X	
PK Sampling ¹¹		X	X	X	X	X
Vital Signs	X	X	X	X	X	

1. Medical history to include disease characteristics as defined in Section 6.1.
2. Screening, yearly while on study, at the subject's last treatment visit and upon relapse
3. For subjects in CR ONLY- may be confirmed with bone marrow biopsy/flow cytometry
4. Until B-cell value is within normal levels (See Section 6.3.1.2.)
5. Prognostic Factors as defined in Section 6.3.3
6. See Section 6.3.2
7. Subjects that are HBsAg negative, HBcAb positive and HBV DNA negative may be included but must undergo HBV DNA monitoring as listed in Section 6.3.4
8. At the subject's last treatment visit
9. Every six months. Igs may be assessed during infection per PI. (See Section 6.3.4)
10. HAHA for ofatumumab treatment only-predose, every six months, at last treatment, and 3& 6 months post last ofatumumab dose, regardless of when it occurs.
(See Section 6.3.4)
11. For pharmacokinetic sampling, see Table 5, Section 6.6; + 15 min window for 0.5h post EOI samples is allowed
12. Only SAEs and associated concomitant medications are to be reported from 60 days after the last dose/observation time. (See Section 6.4.8.)

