#### **Follow-up Phase:**

Survival and disease status assessments (physical examination and evaluation of peripheral blood samples) will be performed post treatment every 3 months for 5 years after last treatment.

Bone marrow examination is required for confirmation of CR at least 2 months post last treatment. MRD assessment will also be performed for subjects demonstrating CR. Subjects with negative MRD will receive follow-up MRD assessment of the peripheral blood until MRD becomes positive. CT-Scans are required for confirmation of CR and PR at least 2 months post last treatment.

Subjects demonstrating disease progression will be followed for survival status until study completion. Follow-up assessment after disease progression on treatment will assess survival status, date of next CLL therapy, type of therapy and response to therapy.

PRO measures (EORTC QLQ-C30, EORTC QLQ-CLL16, EQ-5D and a Health Change Questionnaire) will be administered for completion by the subject at follow-up visits.

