#### **Missing Data**

Missing data occurs when any requested data is not provided, leading to blank fields on the collection instrument. This data will be indicated by the use of a “blank” in subject listing displays. Answers such as “Not applicable” and “Not evaluable” are not considered to be missing data and should be displayed as such.

Since the period of follow-up for any subject will be dependent on efficacy and toxicity, the duration of follow-up will vary among subjects. Consequently, there will be no imputation for missing data. Randomized subjects who do not have any response data will be assumed to be non-responders and will be censored at the date associated with the last visit.

For the PFS endpoint, subjects who are alive and have not progressed at the time of analysis will be censored at the date associated with the last visit with an adequate assessment. If a progression event occurs after an extensive lost-to-follow-up time (more than 2.5 assessment windows), the primary analysis will censor those subjects at the last date of their last visit with an adequate assessment even if subsequent information is available regarding progression or date of death.

Subjects with the designation of treatment relationship for adverse events (AE)s and serious adverse events (SAEs) missing will have the worst case assumed to impute the relationship: if relationship to study treatment is missing it will be assumed to be “Yes”.

There will be no other imputation for missing data other than what’s described in Section 9.2 for partial dates and for missing exposure end dates.

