## **11.2. Secondary Efficacy Analyses**

### **Clinical Benefit:**

- Improvement in response

Improvement in response will be assessed by calculating the percentage of subjects who change from PR at baseline to CR during the study. Improvement in response will also be assessed by providing the frequency and percentage of subjects with negative and positive minimal residual disease (MRD). These rates will be compared between treatment groups with the Cochran-Mantel-Haenszel test adjusting for stratification factors (response at entry, number of prior treatments and type of prior treatment). The 95% confidence intervals will also be calculated for rates in each arm.

- Overall survival

Overall survival is defined as time (in months) from the randomization date to the date of death due to any cause. For subjects who do not die, time of death will be censored at the date of last contact. Survival distributions will be estimated using the Kaplan-Meier method, and survival curves will be compared using a stratified log-rank test. The same analysis will be conducted as described for the primary endpoint, PFS.

The analysis of overall survival will be performed when the second interim analysis for PFS takes place as well as at the end of the study. Subjects will be followed for 5 years after the 2 year treatment period.

- Time to next therapy

Time to next therapy is defined as the time (in months) from the randomization date to the date of receiving the next CLL treatment. For subjects who do not receive another CLL therapy, time of next therapy will be censored at the date of last contact. The same analysis will be conducted as described for the primary endpoint, PFS.

The analysis of time to next therapy will be performed when the second interim analysis for PFS takes place as well as at the end of the study.

- Progression-free survival after next-line therapy

This endpoint will be defined as the time (in months) from randomization until progression or death following next-line therapy and counting as events deaths prior to next-line therapy. Analysis of this endpoint will only include subjects who received next-line therapy and subjects who died prior to receiving next-line therapy. Subjects who receive next-line therapy and who do not have progression or death after next-line therapy will be censored at their last date of contact. If a subject dies prior to next-line therapy, this will count as an event. [REDACTED]

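### MRD retesting stops at the first positive result, but the SAP tabulates MRD status by timepoint with no rule for subjects whose testing has ended

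*SAP*

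**What the plan says.** **Who is tested for MRD.** Protocol 6.2.3 provides for testing at screening in subjects who enter in CR, and after at least two months in subjects who improve to CR on study. Footnote 3 to the Time and Events table (Protocol Appendix 1) limits it in the same way: "For subjects in CR ONLY- may be confirmed with bone marrow biopsy/flow cytometry".

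**When testing stops.** Protocol 6.2.3: "Subjects with negative MRD will receive follow-up MRD assessments of the peripheral blood until MRD analysis becomes positive". The SAP repeats this in Section 3, Follow-up Phase: "Subjects with negative MRD will receive follow-up MRD assessment of the peripheral blood until MRD becomes positive".

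**How MRD is analysed.** SAP 11.2, Disease Markers: "The number and percentage of subjects with positive and negative MRD will be provided at each timepoint". The next sentence compares the positive and negative proportions between arms by a stratified Cochran-Mantel-Haenszel (CMH) test. It names no timepoint and no denominator. Section 11.2 also uses MRD under improvement in response: "Improvement in response will also be assessed by providing the frequency and percentage of subjects with negative and positive minimal residual disease (MRD)". A Kaplan-Meier analysis of time to first positivity is planned, for subjects MRD-negative at baseline.

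**Missing data.** SAP 9.1: "Consequently, there will be no imputation for missing data".

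**Outputs.** Table 2.2070, MRD by timepoint, is omitted from the 280-event analysis but is in the output list of the final-analysis SAP. No time-to-MRD-positivity table or figure is in either list.

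**B cells.** Protocol 6.3.1.2 has monitoring "performed every two months and at every follow-up visit until values return to normal levels on two consecutive determinations". In the Time and Events table the limiting footnote (footnote 4) is attached to the follow-up column only; Visits 3-14 carry no limit.

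**The concern.** A by-timepoint table is read as status: the share of subjects who are MRD-positive or MRD-negative at that visit. Here the result itself decides who is tested next. After a first positive no further test is planned, and with no carry-forward the subject is simply missing from later rows. The rows after the first test then describe those who were negative the last time and have just converted.

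A reader of Table 2.2070 would see a low, flat percentage positive while the true share positive climbs, and would misjudge both the level and the difference between arms. If the CMH test is run on those by-visit data, the treatment comparison has the same fault, and any p-value at or below 0.05 would be labelled nominally significant under SAP 8.4.

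B cells have a related but different problem. In follow-up, subjects whose counts have normalised stop being tested, so late-visit summaries over-represent those who have not recovered.

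**Working it through.** The documents give no MRD or B-cell rates, so there is no planned figure to reproduce. The rates below are assumptions that show the mechanism.

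**MRD, tested-only denominator.** Assume that all subjects start negative, that each converts with probability h per test, and that there are no reversions and no dropout. Testing stops at the first positive.

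- Percentage positive among those tested at test k: h.
- Percentage who have turned positive by test k: 1 − (1 − h)^k.

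At h = 5% (ofatumumab) and 10% (observation), sixth test: 1 − 0.95^6 = 26.5% and 1 − 0.90^6 = 46.9%. The table shows 5% and 10%, a gap of 5 points. The cumulative gap is 46.9 − 26.5 = 20.4 points.

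| Assumed h, ofatumumab / observation | Shown at any test | Cumulative, 6th test | Cumulative, 12th test |
|---|---|---|---|
| 3% / 6% | 3% / 6% | 16.7% / 31.0% | 30.6% / 52.4% |
| 5% / 10% | 5% / 10% | 26.5% / 46.9% | 46.0% / 71.8% |
| 10% / 20% | 10% / 20% | 46.9% / 73.8% | 71.8% / 93.1% |

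**MRD, fixed denominator without carry-forward.** New positives at test k per 100 starting subjects are 100 × (1 − h)^(k−1) × h. At 5% and 10%, 12th test: 100 × 0.95^11 × 0.05 = 2.8 and 100 × 0.90^11 × 0.10 = 3.1. The positive column looks almost equal when 46.0% and 71.8% have converted. The negative column would be right on this denominator if nobody dropped out; the positive column would not.

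**Mixed fast and slow converters.** Let half the observation subjects convert at 30% per test and half at 2%, with both rates halved on ofatumumab. At the 12th test the tested-only table shows 3.2% positive on ofatumumab and 2.7% on observation. The cumulative shares are 48.6% and 60.1%. The displayed contrast has reversed.

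**First tests.** At baseline, or at the first test on reaching CR, nobody has yet been removed by the rule, so those results do show status in the subjects tested.

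**B cells in follow-up.** Assume that all are depleted at the start of follow-up, that a share r recovers to normal per visit, and that testing stops after two normal values. True percentage depleted at visit k is (1 − r)^k. Those still tested are the depleted plus those at their first or second normal value: (1 − r)^k + r(1 − r)^(k−1) + r(1 − r)^(k−2). At r = 10%, visit 8: 0.430 / (0.430 + 0.048 + 0.053) = 81.0% shown, against 43.0%. At r = 5% and 20% the pairs are 90.2% against 66.3%, and 64.0% against 16.8%.

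**The case against.** **The tested-only denominator is not written for efficacy.** The rule that percentages use subjects with a non-missing value at the visit stands in SAP 12.7 and 12.8, which are safety sections. SAP 11 uses the ITT population unless otherwise specified. This is correct, and the tested-only reading is an inference. The positive percentage nevertheless fails on a fixed denominator too, as shown above.

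**The CMH test is not tied to timepoints.** A reader might infer that the arms are tested at every visit in the shrinking set. The text does not say so. If the test uses ever-positive status, a converter has already been counted and little is lost. That makes the test undefined, not demonstrably wrong.

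**The Kaplan-Meier analysis already handles the rule.** For subjects MRD-negative at baseline it does, and under the assumptions above it would return the 26.5% and 46.9%. It leaves out subjects first found negative on study, and it is in neither later output list.

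**CR as a post-randomization outcome.** A reader might infer that the whole MRD denominator is selected by treatment. CR or PR at entry is a randomization stratum, and the CMH test adjusts for it. Only those who improve from PR to CR are selected after randomization.

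**B cells.** It would be wrong to say that these tables show new conversions or compare arms in selected subsets. No between-arm test is planned. The schedule's footnote limits testing in follow-up only. The depletion tables (2.2060, 2.2064) are dropped at 280 events and absent from the final list. What remains exposed is late-visit summaries, such as the change-from-baseline tables (2.2052, 2.2053) kept in the final list.

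**Conclusion.** The point holds for the by-timepoint MRD table after the first test. Result-dependent stopping, no imputation and no rule for subjects whose testing has ended together give a positive percentage that reflects interval conversion and not status. The size depends on assumed rates: at the sixth test, 5% and 10% shown against 26.5% and 46.9% cumulative, and from 16.7% and 31.0% up to 46.9% and 73.8% cumulative over the range tried. These figures assume no reversion and no dropout.

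The B-cell point is smaller: enrichment for non-recovered subjects late in follow-up, in descriptive tables.

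No confirmatory claim is affected. MRD and B cells lie outside the gatekept sequence (SAP 8.4), and the 280-event and final analyses are declared descriptive. The change is still worth making, because the final report would keep the misleading display while its output list includes no time-to-positivity companion.

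**What to change.** **MRD, in SAP 11.2 and the final output list:**

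1. After a first positive, count the subject as MRD-positive at later timepoints unless retested, or report cumulative incidence of positivity.
2. Run the CMH test on that status at a named timepoint with a stated denominator.
3. Show the number tested per visit and arm.
4. Extend time to first positivity to subjects first MRD-negative on study, counted from that first negative test, and add the analysis to the output list.

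**B cells:**

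5. Add a Kaplan-Meier analysis of time to the first of two consecutive normal values for the ofatumumab arm, with the number tested per visit.
6. Reconcile Protocol 6.3.1.2 with footnote 4 of the Time and Events table on when testing may stop.

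**Cost.** SAP wording and a few derivations, with no new data. Carrying a positive forward ignores rare reversions, which should be stated beside the table. Two further steps are matters of choice and are not asked for: counting untested PR subjects as not MRD-negative over all ITT subjects, which mixes response rate with MRD, and treating B-cell recovery as permanent, which assumes values that nobody measured.
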